#### **Decentralized randomized, double-blind, sham-controlled dosing study with Mi-Helper**

A prospective, double-blind, sham-controlled, decentralized, randomized dosing study was conducted to evaluate the efficacy and safety of the Mi-Helper device in adult patients 18 to 65 years of age with episodic migraine with or without aura. The study, deemed Non-significant Risk (NSR) by the Sterling Institutional Review Board, aimed to determine the most effective dose of Mi-Helper compared to sham treatment. The study included a 4-week e-diary run-in period for participant eligibility confirmation and compliance with protocol before randomization.

A total of 172 participants were randomized to one of four treatment arms: three active arms with flow rates of 4, 6, and 10 LPM, and a sham arm. The primary endpoints were pain relief at 2 hours post-treatment, safety (incidence of adverse events), and tolerability (completion of the full treatment session). The safety population included 137 participants, the modified intent-to-treat (mITT) population included 128, and the per protocol (PP) population, which required full treatment compliance, included 74 participants.

The study found that the 10 LPM dose was the most effective, with 71% of participants reporting pain relief at 2 hours post-treatment without the use of rescue medication, and 47% achieving complete pain freedom, compared to only 16% achieving pain freedom in the sham

group ( $p=0.0407$ ). This statistically significant difference in pain freedom between the 10 LPM and sham groups supports further study of the winning Mi-Helper dose. A blinding index confirmed successful blinding across all study arms, including the sham group.

At 24 hours post-treatment, 88% of participants in the 10 LPM group remained pain-free, with all but one subject maintaining pain freedom without rescue medication. No serious or unanticipated adverse device events were reported, and no participants discontinued treatment due to discomfort.

Overall, 82% of participants indicated they would use the Mi-Helper device again outside the study, 53% felt the device worked as well or better than their current rescue medications, and 100% rated the setup and use of the device as "very easy" or "easy."

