### **Treatment Procedures (48 hours)**

Participants will be instructed to use the Mi-Helper device once their migraine head pain has reached at least mild intensity. This will be determined by their response to the question about their head pain within the Study App. Participants will be instructed to use the Mi-Helper within 1 hour from the time of migraine head pain onset.

Once the migraine headache score is recorded as being mild to severe (score of 1 to 3 recorded on the 4-point VRS scale) and the participant has confirmed that they have not used any acute migraine medications in the last 48 hours, the Study App will instruct the participant to initiate treatment with the Mi-Helper device and dose treatment (active or sham) for a total of 15 minutes based on their group allocation. Participants will be advised against using any rescue medication until collection of the Migraine Symptom Questionnaire at 2 hours post-treatment with the Mi-Helper device. However, if participants do need to administer rescue treatment after administering treatment with Mi-Helper, they will need to report this using the 'Rescue Medication Form' within the Study App. Use of rescue medication within 2 hours of treatment will be considered a treatment failure. In the instance that abortive treatments have been used 48-hours prior to the start of treatment or the time of onset of migraine head pain exceeds 1 hour, the participant will need to wait until their next migraine episode of at least mild intensity, to use the device.

Participants will be instructed that they may stop treatment if they are unable to tolerate it by moving the nebulizer away from their nose, and report this within the Study App.

Participants will be required to respond to questions about their head pain, nausea, photosensitivity, phonosensitivity, and the most bothersome symptom (MBS) within the Study App immediately post-treatment and then at 2 hours, 24 hours and 48 hours post-treatment.

At 2 hours post-treatment, participants will also be required to respond to questions about the device tolerability and user experience questionnaire. Select user experience questions will be repeated in the 24-hour assessment.

Participants can report any changes in their health through the Study App while participating in this study.

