3.2.2. Secondary Efficacy Endpoints

- 1. Freedom from Most Bothersome Symptom (MBS) at 2 hours post treatment completion
- 2. Sustained Pain Freedom (SPF) from 2 to 24 hours after treatment completion (defined as pain freedom with no administration of rescue medication and with no recurrence of a mild/moderate/severe headache).
- 3. Pain relief (PR) at 2 hours post-treatment completion (defined as the reduction of severe or moderate pain at baseline to mild or no pain at 2 hours post treatment completion, or from mild pain at baseline to no pain at 2 hours post treatment completion).
- 4. Participants' global impression of acute treatment effect, as measured by the Patient Global Impression of Change (PGIC), on which participants use a 7-point scale, where 1=very much improved to 7=very much worse. Scores of 1 or 2 will be considered successes.

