If migraine symptoms have not resolved, participants will be able to use rescue medication between the 2-to-48-hour period after using the device. Participants will be instructed to report rescue medication use in the 'Rescue Medication Form' within the Study App. This form will be available for participant use during the entire post-treatment period through the Study App and will not be timepoint bound.

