2hr Pain Freedom	Primary Efficacy Endpoint	Baseline Migraine Symptom Questionnaire 2-hour Post Treatment Migraine Symptom Questionnaire	n% Achieved if Head Pain changes from Severe, Moderate, or Mild at baseline to None at 2hrs post-treatment.
2hr MBS Freedom	Secondary Efficacy Endpoint	Baseline Migraine Symptom Questionnaire 2-hour Post Treatment Migraine Symptom Questionnaire	n% Achieved if MBS changes from Severe, Moderate, or Mild at baseline to None at 2hrs post-treatment.
2-24hr Sustained Pain Freedom	Secondary Efficacy Endpoint	Episodic Rescue Medication Questionnaire Baseline Migraine Symptom Questionnaire 2-hour Post Treatment Migraine Symptom Questionnaire 24-hour Post Treatment Migraine Symptom Questionnaire	n% Achieved if Pain Freedom is sustained from 2 hours post-treatment until 24 hours with no administration of rescue medication and with no recurrence of a mild/moderate/severe headache.
2hr Pain Relief	Secondary Efficacy Endpoint	Baseline Migraine Symptom Questionnaire 2-hour Post Treatment Migraine Symptom Questionnaire	n% Achieved if Head Pain changes from Severe or Moderate at baseline to Mild or None at 2 hours post-treatment, OR if Head Pain changes from Mild at baseline to None at 2 hours post-treatment.
Global Impression of Acute Treatment Effect	Secondary Efficacy Endpoint	24-Hour Post Treatment User Experience Questionnaire	Patient Global Impression of Change measure
Rescue Medication use 0-2hrs Post Treatment	Exploratory Endpoint	Episodic Rescue Medication Questionnaire	

		2-hour Post Treatment Migraine Symptom Questionnaire	
0hr Pain Freedom	Exploratory Endpoint	Baseline Migraine Symptom Questionnaire Immediate Post Treatment Migraine Symptom Questionnaire	n% Achieved if Head Pain changes from Severe, Moderate, or Mild at baseline to None immediately post-treatment.
0hr Pain Relief	Exploratory Endpoint	Baseline Migraine Symptom Questionnaire Immediate Post Treatment Migraine Symptom Questionnaire	n% Achieved if Head Pain changes from Severe or Moderate at baseline to Mild or None immediately post-treatment, OR if Head Pain changes from Mild at baseline to None immediately post-treatment.

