8. EFFICACY ANALYSIS

The Pearson Chi-squared test will be used to compare randomized arms with regards to primary and secondary endpoints. Logistic regression modeling will estimate odds ratios and 95% confidence intervals for pain relief/freedom endpoints to compare the two groups. The absolute difference in rates of freedom from pain will be estimated with 95% confidence intervals. Binomial exact 95% confidence intervals will be constructed for the incidence of primary and secondary endpoints within each group.

All statistical analyses will be performed using Stata software (version 19, StataCorp LLC, College Station, Texas).

Deviations from the planned analysis will be described, with proper justification, in the clinical study report.

Type I Error: The overall significance level for this study is 5% using two-tailed tests

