8.2. Secondary Efficacy Analysis

- A hierarchical testing approach will be employed using a fixed-sequence procedure to control type I error due to multiple endpoint testing. The primary endpoint will first be tested and only if $p < 0.05$, will the secondary endpoints be tested. Testing will proceed sequentially, and each endpoint must achieve statistical significance at the 0.05 level to proceed to the next endpoint. If any endpoint in the sequence fails to achieve significance, all subsequent endpoints will not be formally tested and will be considered exploratory.
- The secondary efficacy variables will be summarized by a count and percentage and compared with a chi-squared test. Analysis of secondary endpoints will follow the hierarchical testing approach outlined above to control type I error due to multiple endpoints.
- Global Impression of Treatment Effect will also be summarized by descriptive statistics per treatment group and compared between the groups with a t-test.

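### Sustained pain freedom from 2 to 24 hours requires no recurrence, but the plan names no source that would show an unmedicated headache coming and going between the 2-hour and 24-hour scores

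*SAP*

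**What the plan says.** SAP section 3.2.2 lists 2-24 h SPF second among the secondary endpoints and defines it as pain freedom without rescue and "with no recurrence of a mild/moderate/severe headache". Protocol section 4 defines it in the same terms. SAP Table 1 (section 7.1) repeats the rule: "Achieved if Pain Freedom is sustained from 2 hours post-treatment until 24 hours with no administration of rescue medication and with no recurrence". This is a condition on the whole interval, not on its two ends.

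For this endpoint Table 1 names four sources: the episodic rescue medication questionnaire and the baseline, 2-hour and 24-hour symptom questionnaires. Protocol section 5 (Treatment Procedures) schedules symptom questions "immediately post-treatment and then at 2 hours, 24 hours and 48 hours post-treatment". The Schedule of Events describes head pain as a severity score on a 4-point verbal scale. The rescue form is "available for participant use during the entire post-treatment period through the Study App and will not be timepoint bound" (SAP section 4.1.7), but it is completed when medication is taken.

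For 2-48 h SPF (exploratory), Table 1 lists the rescue form and the baseline, 2-hour and 48-hour questionnaires. The 24-hour questionnaire is not among them.

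SAP section 8.2 sets the gate: "Testing will proceed sequentially, and each endpoint must achieve statistical significance at the 0.05 level to proceed to the next endpoint". The result for 2-24 h SPF therefore decides whether pain relief at 2 hours and PGIC are formally tested.

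**The concern.** The definition asks whether any headache came back. The named sources answer a narrower question: was head pain absent at two moments, and was rescue medication reported? Take a participant who is pain free at 2 hours, has a moderate headache at 8 hours, takes nothing, and scores 0 at 24 hours. By the definition this is a failure. On the listed sources, nothing would distinguish this participant from one who stayed pain free throughout.

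The endpoint carries a stated secondary objective (SAP section 3.1.2) and sits in the gated sequence. If recurrence is not recorded at the time, it cannot be recovered at analysis, so better SAP wording alone would not repair it. What is at stake is the meaning of a durability claim: sustained freedom, or freedom at 2 hours and again at 24 hours without rescue.

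**Working it through.** **1. The plan's own figure.** The documents give no SPF rate. The sample size rests on pain freedom at 2 hours, 41% versus 16%, with 58 per group (SAP section 5). With a pooled proportion of 0.285, the uncorrected formula is n = [1.960·√(2·0.285·0.715) + 0.842·√(0.41·0.59 + 0.16·0.84)]² / 0.25² = 50 per arm. The continuity-corrected version gives 58. Exact Fisher power at 58 per arm is 81.7%. Dropout: 58/0.75 = 77.3, rounded up to 78 per arm, 156 in total. The figure reproduces, and this point does not affect it.

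**2. Definition against sources, 2 to 24 hours.**

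| Event | Named source that would show it |
|---|---|
| Recurrence treated with rescue medication | Rescue form |
| Recurrence still present at the 24-hour score | 24-hour questionnaire |
| Recurrence unmedicated and gone by the 24-hour score | None, unless the 24-hour questionnaire has a look-back item |

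**3. Length of the gap.** The windows in the Schedule of Events are 2 h ± 30 min, 24 h ± 1 h and 48 h ± 2 h.
- 2-24 h: shortest 23 − 2.5 = 20.5 h; longest 25 − 1.5 = 23.5 h.
- 2-48 h on its listed sources: shortest 46 − 2.5 = 43.5 h; longest 50 − 1.5 = 48.5 h. A headache recorded at 24 hours would not enter this derivation.

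**4. Effect on the recorded rates.** Let s be the share of 2-hour pain-free participants recorded as sustained, taken as equal in both arms. Let r be the share of those recorded successes with a missed recurrence. Both are assumptions. Then:
- overstatement, active = 41·s·r points
- overstatement, sham = 16·s·r points
- overstatement of the difference, equal r = 25·s·r points, at most 25r

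The Protocol's account of the previous dosing study says "At 24 hours post-treatment, 88% of participants in the 10 LPM group remained pain-free". The denominator is not stated, so s = 0.88 is used only as an illustration. It gives recorded SPF of 36.1% versus 14.1%, a difference of 22.0 points.

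| r (equal) | Active overstated, s = 0.88 | Sham overstated, s = 0.88 | Difference overstated, s = 0.88 | Difference overstated, s = 1 |
|---|---|---|---|---|
| 5% | 1.8 | 0.7 | 1.1 | 1.25 |
| 10% | 3.6 | 1.4 | 2.2 | 2.5 |
| 20% | 7.2 | 2.8 | 4.4 | 5.0 |

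The active-to-sham ratio stays at 41/16 = 2.56 in every row.

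**5. Unequal missed shares.** The difference is overstated when 41·r(active) > 16·r(sham), that is, when r(sham)/r(active) < 41/16 = 2.56. Above that ratio it is understated. With s = 0.88 and a recorded difference of 22.0:
- 20% active, 10% sham: true difference 16.2 points
- 10% active, 20% sham: 21.2 points
- 10% active, 30% sham: 22.6 points (understated by 0.6)

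**6. The test.** When the recorded SPF rates are equal in the two arms, the Pearson chi-squared test at 58 per arm has exact size 4.6% to 5.3% for common rates from 5% to 36%. Exact power at the illustrative recorded rates is 80.1%. At the corresponding true rates with equal r it is 77.4% (r = 5%), 74.6% (10%) and 68.2% (20%).

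**The case against.** The strongest reply is that the written rule is right: it calls any recurrence a failure, and nothing in the documents says SPF is computed from two scores alone. A reader might infer that the plan itself counts a returned-and-cleared headache as success. The text does not say so. What stands is that the rule has no named data behind one of its clauses, so the misclassification would arise from what is collected.

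Second, the items of the 24-hour questionnaire are not reproduced. A single look-back question there would remove the data gap, and only the derivation line would be missing. This stands, and the point is conditional on it.

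Third, one cannot say flatly that no diary runs after treatment. The Protocol synopsis mentions eDiary training after shipment, and Protocol section 7.3 refers to the treated headache being recorded in the eDiary. However, the Schedule of Events shows only a 28-day run-in eDiary, and Table 1 names no diary as a source. Participants can also report changes in health through the app, but Table 1 does not use those reports either.

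Fourth, a reader might infer that the device's durability result is inflated. The documents do not support this as a general statement. Both arms' recorded rates can only rise, but the effect on the difference depends on arm-specific missed shares that no document gives. Nor is this a demonstrated loss of type I error control: the test keeps its size when recorded rates are equal.

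**Conclusion.** The point holds in conditional form and should be fixed, with medium confidence. As documented, the no-recurrence clause of 2-24 h SPF has no named measure for unmedicated headaches that resolve within a gap of 20.5 to 23.5 hours. Unless an unseen look-back item exists, such headaches would be recorded as successes against the definition, and the result would support only freedom from pain at 2 hours and at 24 hours without rescue.

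For equal missed shares of 5% to 20%, the difference is overstated by 1.1 to 4.4 points at s = 0.88, and by 1.25 to 5.0 points at the upper limit s = 1. These sizes rest on the plan's 41% and 16%, an equal sustained share in both arms, and an assumed r. The 2-48 h endpoint shares the problem, and its source list also leaves out the 24-hour questionnaire.

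**What to change.** 1. Confirm that the 24-hour and 48-hour app questionnaires ask whether there has been any headache since the last report and, if so, its worst severity. If they do not, add that one item at both time points.
2. In SAP Table 1, state that 2-24 h SPF is not achieved if the 24-hour item is positive, and that 2-48 h SPF is not achieved if either item is positive.
3. Add the 24-hour questionnaire to the sources for 2-48 h SPF, so that any head pain recorded at 24 hours is a failure.
4. If the item cannot be in place for every participant, do not mix two definitions in the gated test. Use one definition for everyone, label it *pain free at 2 h and at 24 h without rescue*, and report the recall-based version as supportive.

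The cost is at most one question at two existing time points and a few lines in Table 1. The downsides are some recall error and a slightly less favourable sustained rate. Delay costs more, because recurrence in participants already treated cannot be recovered reliably later.

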7.2. Participant Disposition

Participant disposition will be summarized by study group and overall using Screened, Enrolled, ITT (Randomized/Safety Population), mITT, and PP populations. The number and percentage of participants for each study product will be presented for ITT, mITT, and PP populations. The denominator for percentages will be the number of participants randomized per group.

Discontinued participants will be summarized by product group and overall based on discontinued reasons.

A listing for disposition will include the participants who are randomized and will cover the following information: population assigned (ITT, mITT, and PP), study completion status and reason for discontinuation/screen failure.

7.3. Demographics and Baseline Characteristics

Age and other continuous demographic and baseline variables will be summarized using descriptive statistics such as mean, range, median and standard deviation. Age group, gender, race, ethnicity, and

other categorical demographic and baseline variables will be summarized using frequency counts and percentages for the ITT, mITT, and PP populations.

7.4. Protocol Deviations

A summary table and a listing for individual participants will be presented to describe the significant protocol deviations for this study based on the safety population.

7.5. Prior and Concomitant Medications

Concomitant medications taken during the study will be listed for the ITT population by participant. The listing will include reason for the medication as well as the start and stop date/time.

7.6. Concurrent Illnesses and Medical Conditions

Medical Histories will be listed for the Safety Population by System Organ Class (SOC) and Preferred Term (PT).

7.7. Descriptive Statistics

Descriptive statistics of the quantitative variables will be summarized using number of participants with non-missing observations (n). The qualitative variables will be summarized using counts and percentages of participants in each category. Summaries will be presented by the treatment group and time point (where relevant) for the ITT, mITT and Per Protocol Populations.

Study Product exposure and concomitant medications will be summarized using counts and percentages of participants by treatment group for the safety population.

8. EFFICACY ANALYSIS

The Pearson Chi-squared test will be used to compare randomized arms with regards to primary and secondary endpoints. Logistic regression modeling will estimate odds ratios and 95% confidence intervals for pain relief/freedom endpoints to compare the two groups. The absolute difference in rates of freedom from pain will be estimated with 95% confidence intervals. Binomial exact 95% confidence intervals will be constructed for the incidence of primary and secondary endpoints within each group.

All statistical analyses will be performed using Stata software (version 19, StataCorp LLC, College Station, Texas).

Deviations from the planned analysis will be described, with proper justification, in the clinical study report.

Type I Error: The overall significance level for this study is 5% using two-tailed tests

8.1. Primary Efficacy Analysis

- Pain freedom at 2 hours is defined as the reduction in head pain to “none”, i.e., from severe, moderate, or mild head pain to none. Pain will be rated on a scale from 0 to 3, where 0 is no pain and 3 is severe pain. Pain freedom will compare the active arm to the sham arm using a Chi-squared test.
- Use of rescue medication prior to 2 hours post treatment completion will be considered a failure for this endpoint (i.e., patient will be assigned the status of no reduction).
- A sensitivity analysis of the primary endpoint will be performed to assess the impact of missing data on the study outcome. This will be done on the ITT analysis set, where missing 2-hour pain assessment is considered not to be pain free.

- Subgroup analyses will be conducted to evaluate whether treatment effects on the primary endpoint differ by gender, age group, use of preventive medications, and baseline headache severity. These analyses will help assess the generalizability of the treatment effect across diverse patient populations.

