4.1.6. Baseline Procedures (pre-treatment)

Baseline assessments will be initiated at the onset of a migraine attack. Baseline assessments will include questions about the participant's head pain, nausea, photosensitivity, phonosensitivity, and the most bothersome symptoms (MBS) which will be recorded within the Study App prior to treatment initiation.

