4.3. Randomization and Blinding

For this study, a total of 156 participants will be randomized equally into two groups. 1:1 randomization will be performed with a block size of 6, and stratified by gender to ensure balance with regards to gender.

- Group I (active treatment): 10 LPM, dehumidified air, 15 minutes
- Group II (sham [control] treatment): 2 LPM, ambient air administered intermittently via Mi-Helper, 15 minutes total

Balance between the two arms will be evaluated and confirmed using standardized mean differences (SMD), where absolute SMD values less than 0.2 will be considered as indicating good balance on a given variable or confounder. For variables that have an absolute SMD larger than 0.2, adjustments may be made to minimize any possible imbalance on those variables using multivariable analysis.

Participants will be randomized in a 1:1 fashion, with stratification for gender. The randomization schema for this study will be implemented within the ObvioGo platform.

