6. GENERAL ANALYSIS CONSIDERATIONS

6.1. Analysis Populations

For the purposes of analysis, the following analysis sets are defined:

6.1.1. *Intent-to-Treat (ITT) Population*

- All participants who were randomly assigned to a treatment.

6.1.2. *Modified Intention to Treat (mITT) Population*

- All participants who used the study intervention and completed a baseline and 2-hour post-dose pain assessment.

6.1.3. *Per Protocol (PP) Population*

- All participants in the mITT population that do not have a major protocol deviation related to primary endpoint(s), and completed the primary endpoint(s) and completed the treatment in compliance with the protocol, with group assignment as treated.

The ITT analysis set will serve as the main analysis set for all safety evaluations.

The mITT analysis set will be the primary population used for efficacy analyses in this study.

The primary and secondary efficacy assessments will also be performed on the PP and the ITT analysis sets as a sensitivity analysis.

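### The primary chi-square is sound, but the logistic model names no covariates and adjustment rests on an optional SMD trigger; fixing gender and baseline head-pain grade in advance is a nearly free gain

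*SAP*

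**What the plan says.** - **Primary test.** SAP 8: "The Pearson Chi-squared test will be used to compare randomized arms with regards to primary and secondary endpoints". SAP 8.1 repeats it for pain freedom: "Pain freedom will compare the active arm to the sham arm using a Chi-squared test". Protocol 11.6.1 agrees.
- **Logistic model.** SAP 8: "Logistic regression modeling will estimate odds ratios and 95% confidence intervals for pain relief/freedom endpoints to compare the two groups". No covariate is listed.
- **Stratification.** SAP 4.3: "1:1 randomization will be performed with a block size of 6, and stratified by gender to ensure balance with regards to gender".
- **Baseline pain.** SAP 4.1.6: "Baseline assessments will be initiated at the onset of a migraine attack". The answers are entered before treatment starts, and treatment needs a grade of 1 to 3 (SAP 4.1.7). The mITT set is "All participants who used the study intervention and completed a baseline and 2-hour post-dose pain assessment", so the grade is complete there, and also in the PP set, which is drawn from mITT.
- **Adjustment rule.** SAP 4.3: "For variables that have an absolute SMD larger than 0.2, adjustments may be made to minimize any possible imbalance", by multivariable analysis. It lists no variables and does not say whether the result is primary, sensitivity or supportive. Protocol 11.2 has the SMD check but no adjustment step.
- **Where the two variables do appear.** In the efficacy plan, gender and baseline headache severity enter only as subgroup factors for the primary endpoint (SAP 8.1, Protocol 11.6.1).
- **ITT sensitivity analysis.** SAP 8.1: "This will be done on the ITT analysis set, where missing 2-hour pain assessment is considered not to be pain free".

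**The concern.** Two baseline variables are available at no data cost: the randomisation stratum and the pre-treatment grade of the symptom that defines the endpoint. Listing both as subgroup factors shows that the sponsor thinks them relevant, but a subgroup analysis does not adjust the main comparison.

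Instead, whether to adjust, and for what, is decided after looking at imbalance, by a rule that often fires by chance. Adjusted and unadjusted results can fall on opposite sides of 0.05, and the primary result decides whether the fixed sequence of secondary endpoints opens (SAP 8.2). An adjusted result of unstated standing next to it invites an avoidable argument. What is at stake is some precision and a cleaner pre-specification, not the validity of the primary test.

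**Working it through.** **Inputs from the documents.** Two-sided 5% level; 41% active v 16% sham; 58 evaluable per arm; 25% dropout; 156 randomised (SAP 5 and 8); blocks of 6 within gender (SAP 4.3).

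**Assumed, because the documents give none.** Gender mix 92 women and 24 men; mild/moderate/severe 35/45/20%; a fixed step in log-odds of pain freedom per pain grade of 0, 0.5, 1.0 or 1.5. Other mixes were also run.

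**1. The plan's own sample size.** The continuity-corrected two-proportion formula gives 58 per arm. Exact two-sided Fisher power is 81.7% at 58 (79.9% at 56). 58/0.75 = 77.3, so 78 per arm and 156 in total. The stated figures reproduce.

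**2. The planned chi-square.** Summing the two binomial distributions exactly, Pearson test without correction:
- 58 per arm, 0.41 v 0.16: power 86.4%.
- Size: 5.12% at a common rate of 28.5%, and 5.16% at 16%.
- ITT with 20 of 78 per arm missing and counted as failures: 0.41 × 58/78 = 0.305 v 0.16 × 58/78 = 0.119; power 82.9%.

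**3. How often the SMD rule fires by chance.** For a variable outside the stratification, the observed SMD is roughly normal with mean 0 and standard deviation √(2/n), so P(|SMD| > 0.2) = 2[1 − Φ(0.2/√(2/n))].
- n = 58: 0.2/0.1857 = 1.077, giving 28%.
- n = 78: 0.2/0.1601 = 1.249, giving 21%.

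As no variable list exists, no overall rate can be stated.

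**4. Fixed adjustment.** Simulation with 20,000 trials per scenario and arm rates held at 41% and 16%. The model is logistic with treatment, gender and pain grade, tested by the score test.

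| Step per grade (assumed) | Score test | Chi-square | Paired difference, points |
|---|---|---|---|
| 0 | 86.0% | 86.0% | 0.0 |
| 0.5 | 87.6% | 86.9% | +0.7 |
| 1.0 | 88.6% | 86.1% | +2.5 |
| 1.5 | 91.4% | 86.4% | +5.0 |

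Monte Carlo standard error of the difference: 0.08 to 0.19 points. Other assumed gender and severity mixes gave −0.1 to +2.7. Adjusting for gender alone moved power by only 0.1 to 0.5 points.

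**5. Which test.** Size under the null:
- score 5.1–5.5%
- likelihood-ratio 5.3–6.0%
- Wald 4.5–5.2%
- chi-square 5.0–5.3%

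Wald power differs from chi-square by −0.7 to +4.5 points. A separate simulation of a Cochran–Mantel–Haenszel test stratified by gender and severity gave about −2 to +4 points. The choice of test therefore matters and should be named.

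**6. Effect measure.** The 95% interval for a standardised risk difference covers 93.8–94.7% of the time (unadjusted 94.0–94.9%). Its standard deviation is 0.5% larger at step 0 and 7.6% smaller at step 1.5. The marginal odds ratio is (0.41/0.59)/(0.16/0.84) = 3.65. The conditional one is about 3.8 at step 0.5, 4.0–4.2 at 1.0 and 4.7 at 1.5.

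**7. Disagreement.** Under the planned effect, score test and chi-square differ on significance in 1.3–7.4% of simulated trials. If either could be claimed whenever the SMD rule fired on severity alone, type I error would rise by about 0.3–0.6 points.

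**The case against.** The strongest reply is that nothing needs repair. The chi-square is valid, is named consistently in both documents, and exceeds the planned 80% power. SAP 8.2 puts the primary endpoint first, and SAP 8 requires departures from the plan to be justified in the study report. Gender adds almost nothing. The +5-point gain needs 1.5 log-odds per grade, which over the two steps from mild to severe is an odds ratio of e³, about 20. All of this stands, and it limits the point to an improvement.

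Four stronger readings are tempting, and the documents do not support them:
- *The primary test is wrong because it ignores the stratum.* Its size is close to 5% without it.
- *The order of adjusted and unadjusted tests is open.* The chi-square is fixed as primary. The SMD sentence sits in the randomisation section, and nothing there lets an adjusted result replace it, so the error inflation in step 7 is hypothetical.
- *There is no model at all.* SAP 4.3 says multivariable analysis, and SAP 8 names logistic regression. The covariates and the standing of the result are what is missing.
- *Protocol 11.2 calls for the SMD check before any attack baseline exists.* Its wording can equally mean any time after randomisation, including at analysis.

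What the reply does not answer is the trigger itself: it fires often by chance, with no variable list and no stated role for the result.

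**Conclusion.** The point holds as an efficiency and pre-specification improvement worth making, not as an error. The SMD part needs no assumption about prognosis: under correct randomisation the rule fires for 28% of unstratified variables at 58 per arm and 21% at 78, and the standing of the result is unstated. The natural reading is that such an adjustment is supportive, but the SAP should say so.

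The power part is conditional. With the score test the change is about 0 if pain grade is not prognostic, about +0.7 points at 0.5 log-odds per grade, about +2.5 at 1.0 and +5.0 at 1.5. These figures rest on assumed gender and severity mixes. Almost all of any gain comes from pain grade; gender contributes at most about 0.5 points.

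**What to change.** 1. **mITT and PP.** Specify the planned logistic regression with treatment, gender and baseline head-pain grade (1–3) as fixed covariates. Name the score test for treatment. Report a standardised risk difference with 95% CI beside the conditional odds ratio.
2. **Standing.** State one of two options: this model is the primary test with the chi-square as named sensitivity analysis, or the chi-square stays primary with this model as the single named supportive analysis.
3. **Secondary endpoints.** Apply the same choice to the pain-based endpoints in the fixed sequence (sustained pain freedom from 2 to 24 hours, pain relief at 2 hours). Name the baseline covariate for freedom from the most bothersome symptom, and say which test applies to PGIC success.
4. **SMDs.** Make them descriptive and delete the sentence that allows adjustment above 0.2.
5. **ITT.** Adjust for gender only, because untreated participants have no attack baseline. Report the unadjusted chi-square in both ITT and mITT, so that the missing-data comparison is like for like.

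**Cost.** SAP wording and a few lines of code before unblinding; no new data. The downsides are that the odds ratio becomes conditional, and that the ITT model cannot include severity: at the planned dropout up to 156 − 116 = 40 participants could lack a baseline grade. The standardised risk difference answers the first, and the chi-square in both sets answers the second.
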